8.0 Study Withdrawal/Discontinuation

A study subject will be discontinued from participation in the study if any of the following occur:

- Unacceptable adverse event (AE)
- Intercurrent illness, or other medical condition or situation occurs such that continued participation in the study would not be in the best interest of the subject in the opinion of the treating investigator
- Development of any exclusion criteria
- Subject withdraws consent to continue in the research for any reason

Handling of Withdrawals

Subject will be followed as per standard of care, after withdrawal from study.

Termination of Study

Possible reasons for discontinuation of the study include poor study accrual and/or IRB request for study closure after review of reported adverse event(s) in the required timeline as above.

9.0 Statistical Considerations

This is an un-blinded, single center, randomized controlled trial. The associations between categorical variables and the arms will be analyzed with Fisher's exact test; Mann-Whitney and Kruskal-Wallis tests for continuous variables. p values will be obtained by the two-sided exact method at the conventional 5% significance level. Using an intention to treatment power analysis for Aim 1, a sample size of 62 patients (31 per arm) will be required to detect a 30% absolute increase in the detection rate of csPCa, with a one-sided 0.05 significant level, a type II error of 0.20, and the rate of csPCa being 18.1% from standard biopsy,⁷ based on two-sample test for proportions. For Aim 2, assuming about 25% of Arm A is MRI- and rate of csPCa was 4% in MRI- and 48% in MRI+ (based on the results from paper published by Porpiglia et al⁷) and using one-way ANOVA test, it will require 72 patients (36 per arm) to detect this difference with power of 80%. Considering 10% of patients will be lost to follow-up, the total sample size needed will be 80 patients. No interim analyses will be planned, and all procedures will be performed on an intention-to-treat basis for Aim 1 as our main analyses. Non-intent to treat analyses under Aim 2 will be treated as sensitivity analyses. All analyses will be performed with SAS version 9.4 (SAS Institute, Cary, NC).

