4.0 Treatment Assignment/Randomization

Enrollment into the study is defined as following randomization. Patients who fulfill all eligibility criteria and have provided written consent will be randomized to undergo mpMRI followed by targeted biopsies (arm A mpMRI+) or TRUS transrectal biopsy (arm-B) by the PI and authorized study collaborators. [REDACTED], study coordinator, will have access to randomization, generated by an electronic randomization system provided by REDCap.

Sequence generation

Patients will be randomly assigned to arm A or arm B following a 1:1 simple randomization procedure according to a computer-generated randomization list provided by REDCap. [REDACTED] [REDACTED] study coordinator, and a designated back-up will be the only persons to have access of the REDCap randomization list.

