Data analysis will be done by [name] (Department of Surgery analyst) supervised by [name] (PI) and statistical analysis collaborators ([name], IRB approved). Data to be analyzed will be de-identified will have no protected health information (PHI) including patient name, medical record number or date of birth.

PRE-PROCEDURE EVALUATION (within 2 months from study enrollment)

Patients are going to be evaluated at the time of office appointment by the PI and Study Collaborators

- Screening-Patients with elevated level of Prostate-specific antigen (PSA >1 ng/ml but <15 ng/ml), will be screened for research study participation by the urology providers (Co-Investigators) and [name] (PI).
- Inclusion/ Exclusion Criteria
- Consent- Patient having all the inclusion and no exclusion criteria for eligibility will be approached with research consent for participation by the urology providers (Co-Investigators) and [name] (PI).
- Demographics
- Medical History
- Surgical History
- Clinical Stage/ Digital Rectal Exam
- Vital Signs
- Physical Exam
- MRI PI-RAD Score (Grade System to classifying prostate cancer , using Pre-Procedure MRI (within 2 months from consenting & randomization))- only required for arm A
- Gland Volume (Calculated from the mpMRI and/or Ultrasound -within 2 months from consenting & randomization)
- Prostate specific antigen (PSA)

PROCEDURE EVALUATION (Surgical procedure)

Patient will undergo prostate biopsy in arm A or arm B as assigned by the randomization card

- A. Transperineal mpMRI-targeted prostate biopsy (arm A mpMRI+) (Procedure will be performed in operating room):** mpMRI-targeted prostate biopsy is standard of care and will be performed using the UroNav transperineal fusion system by a single urologist ([name]). [name] has >1 yr experience in performing mpMRI-targeted prostate biopsies. All patients will receive one dose of Ancef intravenous antibiotic at time of surgery (Vancomycin 1gm intravenous for penicillin/cephalosporin allergies or prior history of orthopedic hardware implanted within 2 years) to cover skin flora and may add additional antibiotic if prior documented UTI(s) in past then antibiotic may be tailored according to those culture(s) sensitivities) to cover enteric flora as well. All patients will receive an enema until result to be performed the morning of prostate biopsy.

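### The unadjusted two-sided Fisher test for the primary endpoint gives away about 7 points of power through conservatism; adjusting for baseline PSA might add a further 0 to 7

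*Combined protocol and SAP*

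**What the plan says.** Section 9.0 states that "The associations between categorical variables and the arms will be analyzed with" Fisher's exact test, and that "p values will be obtained by the two-sided exact method at the conventional 5% significance level". It names no stratified or covariate-adjusted analysis. Intention to treat is the main analysis for Aim 1.

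For Aim 1 the plan states that "a sample size of 62 patients (31 per arm) will be required". The target is a gain of 30 percentage points over an assumed 18.1% with standard biopsy. The sizing was done "with a one-sided 0.05 significant level, a type II error of 0.20". Aim 2 raises the number to 72 (36 per arm), and 10% loss to follow-up brings it to 80.

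Section 4.0 specifies a "1:1 simple randomization procedure", with no blocks or strata. PSA between 1 and 15 ng/ml is an entry criterion (Section 3.0), and the schedule of events in Section 5.0 collects it pre-study in both arms. Sections 2.0 and 5.0 word the primary contrast as arm A mpMRI+ against arm B. They include PSA density in the csPCa definition for standard biopsy but not for targeted biopsy.

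**The concern.** Two features of the chosen test cost power. First, Fisher's test is discrete, and in samples this small it rejects much less often than its nominal 5%. Second, it ignores a baseline value that every man has and that may predict the outcome. Randomisation does not balance that value either.

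The trial has no power to spare. It was sized one-sided but will be tested two-sided, so a true 30-point difference is more likely to be missed than the plan implies. A chance PSA imbalance among about 80 men would also stay in the unadjusted estimate.

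**Working it through.** **Reproducing the plan's figure.** Inputs from Section 9.0: p1 = 0.181, p2 = 0.481, one-sided alpha 0.05, power 80%. The pooled two-proportion formula is

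n = [1.645·√(2·0.331·0.669) + 0.842·√(0.181·0.819 + 0.481·0.519)]² / 0.30² = (1.095 + 0.531)² / 0.09 ≈ 29.4.

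This gives 30 per arm, or 60 in total, within two patients of the stated 62. The total also reproduces: 72 / 0.90 = 80.

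**Power of the planned test, 48.1% vs 18.1%** (Fisher by full enumeration):

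| Test | 31 per arm | 36 per arm |
|---|---|---|
| One-sided z (the sizing basis) | 81.9% | 86.8% |
| Two-sided z | 71.9% | 78.4% |
| Two-sided Fisher (planned) | 63.5% | 71.3% |

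At 36 per arm, going from one-sided to two-sided costs 86.8 − 78.4 = 8.4 points, and Fisher's conservatism costs 78.4 − 71.3 = 7.1. Fisher's true size at 36 per arm is 2.5% when both rates are 18.1%, and 2.8% when both are 33.1%.

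**Alternatives at 36 per arm, two-sided 5%.** The second scenario uses the blended arm A rate from the Aim 2 inputs: 0.75 × 48% + 0.25 × 4% = 37%. The adjusted test takes residuals from a regression of csPCa on the baseline covariate, ignoring arm. It then compares their arm A sum with its distribution over 999 re-randomised assignments (3,000 simulated trials per setting). The PSA odds ratio per SD is an assumption; the documents give none.

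| Test | 48.1% vs 18.1% | 37% vs 18.1% |
|---|---|---|
| Fisher | 71.3% | 34.2% |
| Mid-p Fisher, unadjusted | 77.2% | 42.5% |
| Boschloo, unadjusted | 78.8% | 43.6% |
| Re-randomisation, PSA OR 1.0 | 79% | 42% |
| Re-randomisation, PSA OR 1.5 | 79% | 42% |
| Re-randomisation, PSA OR 2.0 | 81% | 47% |
| Re-randomisation, PSA OR 2.5 | 84% | 48% |

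A repeat simulation gave 78%, 80%, 81% and 85% in the first scenario and 43%, 43%, 49% and 48% in the second. The Monte Carlo standard error is about √(0.8 × 0.2 / 3,000) = 0.7 points, so one-point differences mean nothing. Across all runs the adjusted test reached 41% to 50% in the second scenario. Its simulated size was about 5% (4.7% to 5.2% in the two main sets of runs).

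**Splitting the gain (48.1% vs 18.1%).**
- Removing conservatism: Boschloo minus Fisher is 78.8 − 71.3 = 7.5 points. The re-randomisation test gains about the same when the covariate is pure noise.
- PSA's own share, OR 2.5 against OR 1.0: 84 − 79 = 5 points in one simulation and 85 − 78 = 7 in the other. At OR 1.5 it is about nil. The variance of the standardised risk difference falls by about 2%, 6–7% and 12–13% at ORs of 1.5, 2.0 and 2.5.
- A separate simulation drew PSA on its eligible range, with odds ratios of 1 to 4 per doubling (AUC 0.50 to 0.73). It also put PSA's share at about 0 to 7 points, and at 3 or fewer unless the AUC exceeds about 0.62.

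**The method matters.** An exact test stratified at the PSA median or tertiles gains only about 2 to 8 points over Fisher in total, because it remains discrete.

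**The case against.** An unadjusted, prespecified exact test is valid in a trial this small, so preferring another is a matter of efficiency. That stands: nothing in the plan is wrong on this point. Chance imbalance under randomisation is also not bias, and Fisher's error rate already allows for it.

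A reader might infer that ignoring PSA itself costs the full gain of 7 to 14 points. The documents do not support that. About 7 points appear when PSA carries no information and can be had from an unadjusted test. The rest depends on a prognostic strength that no section states.

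A reader might also infer that the change is free and applies to the primary contrast as worded. Neither is so. Membership of arm A mpMRI+ is known only after allocation and is never observed in arm B, so no set of re-randomised assignments exists for that contrast. The test is justified only for the full randomised arms, which is what the intention-to-treat sentence in Section 9.0 calls for.

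Finally, PSA density enters the csPCa definition for standard biopsy only, so PSA helps to define the outcome mostly in one arm. This asymmetry affects Fisher's test equally and does not break the re-randomisation null, because PSA is fixed before allocation. It does complicate the adjusted estimate, and the simulations assumed one common PSA effect.

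**Conclusion.** The point holds as a cheap improvement to the analysis, not as an error that invalidates it. With 36 evaluable men per arm and the design rates, the planned test has about 71% power at a true size of about 2.5%. A less conservative test recovers about 7 points. PSA adjustment may add about 0 to 7 more, assuming an odds ratio of 1.0 to 2.5 per SD.

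It would be wrong to conclude that the change restores the planned power. At the blended rate of 37%, power rises from about 34% to at most about 50%. The mismatch between one-sided sizing and two-sided analysis is the larger problem and needs its own correction.

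**What to change.** Before any outcome data are seen (the trial is unblinded), amend Section 9.0 as follows:

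- **Primary test:** regress csPCa on log baseline PSA ignoring arm, take the residuals, and compare their arm A sum with its distribution over re-randomised assignments, two-sided at 5%. State the number of re-randomisations and the seed.
- **Population:** all men randomised to arm A against all men randomised to arm B. Reconcile the primary endpoint wording in Sections 2.0 and 5.0 with this.
- **Estimate:** the PSA-standardised risk difference with a 95% confidence interval.
- **Sensitivity analysis:** the Fisher test as now planned.
- **Endpoint:** apply one csPCa definition alike to both arms, or say that the adjusted estimate will be read with caution because PSA density enters the standard-biopsy definition only.
- **Covariates:** do not add gland volume, which the schedule of events takes from MRI in arm A and ultrasound in arm B.

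If an adjusted test is not wanted, an unadjusted Boschloo test secures the first 7 points or so.

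The cost is about a paragraph of text, a little more SAS programming and a less familiar primary test. No extra patients, visits or measurements are needed.

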No study has compared UroNav transperineal mpMRI-targeted versus standard transrectal prostate biopsy in the detection of prostate cancer.

The **hypothesis** being tested is that computerized fusion guided biopsy (**UroNav**) will increase detection of csPCa compared to standard biopsy (SB) (transrectal) alone. The primary end point will be the comparison of detection rates csPCa between arm A mpMRI+ and arm B (refer to figure on page 9). csPCa will be defined according to the Standards of Reporting for MRI-targeted Biopsy Studies (START) criteria for targeted biopsy Gleason Score ≥ 7 or maximum cancer core length (CCL) ≥ 5 mm and the updated Epstein criteria for SB (Gleason score ≥ 7 , PSA density ≥ 0.15 , Gleason score ≥ 2 positive cores, and bilateral cancer).^{2,3} The secondary end points will be (1) comparison of the overall detection rate of PCa and csPCa between arm A mpMRI+, arm A mpMRI-, and arm B and (2) comparison of complication rates (Table 2) between arm A mpMRI+ and arm B.

Considering 10% of patients will be lost to follow-up, the total sample size needed will be 80 patients (See Section 9.1 Statistical Considerations). The clinical trial is enrolled in clinicaltrials.gov (**ClinicalTrials.gov Identifier NCT03044197**).

If the primary end point is reached, the study will continue and remain ongoing to examine the remaining secondary end points.

Specific Aims:

1. Determine if UroNav increases the detection of csPCa between arm A mpMRI+ than arm B standard transrectal biopsy.
2. Determine if UroNav increases the overall detection of PCa between arm A mpMRI+ versus arm A mpMRI- and arm B standard transrectal biopsy.
3. Determine if UroNav decreases rates of complications between arm A mpMRI+ than arm B standard transrectal biopsy.

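### Aim 1 is sized one-sided at 5% but the declared test is a two-sided 5% Fisher exact test, whose power at 72 evaluable patients is about 71% to 74%, below the 80% target

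*Combined protocol and SAP*

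**What the plan says.** All the relevant statements are in Section 9.0 (Statistical Considerations) of the combined protocol and SAP.

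- Analysis test: "The associations between categorical variables and the arms will be analyzed with Fisher's exact test".
- Level and sidedness of the analysis: "p values will be obtained by the two-sided exact method at the conventional 5% significance level".
- Sizing of Aim 1: 62 patients (31 per arm) for a 30-point absolute increase over 18.1%, "with a one-sided 0.05 significant level, a type II error of 0.20", "based on two-sample test for proportions".
- Sizing of Aim 2, which sets the trial size: "it will require 72 patients (36 per arm) to detect this difference with power of 80"%. Allowing for 10% loss, this becomes 80 patients.

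Detection of csPCa is a categorical outcome compared between arms, so the Fisher and two-sided rules cover it as written. Sections 1.0 and 2.0 word the hypothesis directionally (targeted biopsy will increase detection), but no sentence makes the Aim 1 test one-sided. Section 4.0 specifies 1:1 simple randomization, so the arms need not be equal in size.

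**The concern.** The primary comparison is sized under one decision rule and declared to be analysed under a stricter one. Two things change between the sizing and the analysis: the level goes from one-sided 5% to two-sided 5%, and the test goes from a large-sample comparison of proportions to Fisher's exact test, which is conservative at this size. Both changes lower power, so the stated type II error may not apply to the test that will be run.

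The decision rule is also left open to argument. In an un-blinded trial with two candidate rules on paper, a result that is positive under one and negative under the other would be hard to defend either way.

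**Working it through.** **Inputs (Section 9.0).** Control rate p2 = 0.181; increase 0.30, so p1 = 0.481; type II error 0.20; 31 per arm for Aim 1; 72 evaluable (36 per arm) from Aim 2; 72 / 0.90 = 80 randomized.

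**Step 1: reproduce the 31 per arm.** Pooled two-proportion formula, with mean rate p = (0.481 + 0.181)/2 = 0.331:

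n = [z_α √(2p(1−p)) + z_β √(p1(1−p1) + p2(1−p2))]² / (p1−p2)²

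Here √(2 × 0.331 × 0.669) = 0.6655, √(0.2496 + 0.1482) = 0.6308, z_β = 0.8416, and (p1−p2)² = 0.09.

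- One-sided 5% (z = 1.645): (1.0947 + 0.5309)² / 0.09 = 29.4, so 30 per arm.
- Two-sided 5% (z = 1.960): (1.3044 + 0.5309)² / 0.09 = 37.4, so 38 per arm.

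The stated 31 agrees with the one-sided level (power at 31 by the same formula is 81.9%) and not with the two-sided level (71.9%). The 62 is not a miscalculation under its own inputs.

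**Step 2: power of each rule at 36 per arm.** For every pair of counts (x1, x2), apply the test and sum the product of the two binomial probabilities over the pairs that reject.

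| Test at 36 vs 36 | One-sided 5% | Two-sided 5% |
|---|---|---|
| Pooled z-test, enumerated | 87.5% | 80.0% |
| Fisher's exact test | 81.5% | **71.3%** |

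By the normal formula the two-sided z-test has 78.4%. Either change alone leaves power near or above 80%. The declared combination does not.

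**Step 3: the declared test at each planned size.** The averages weight each split of N by its probability under 1:1 simple randomization.

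| Evaluable N | Two-sided Fisher, equal arms | Two-sided Fisher, averaged | One-sided Fisher, equal arms |
|---|---|---|---|
| 62 (stated for Aim 1) | 63.5% | 66.2% | 74.6% |
| 72 (after 10% loss) | 71.3% | 74.4% | 81.5% |
| 80 (no loss) | 76.3% | 78.7% | 85.1% |

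With equal arms the declared test first reaches 80% at 43 per arm (79.4% at 42, 80.7% at 43). That is 86 evaluable, or 86 / 0.90 = 95.6, about 96 randomized.

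**Step 4: can the two rules disagree?** For 15/36 vs 7/36, Fisher gives p = 0.036 one-sided and p = 0.072 two-sided. At 48.1% vs 18.1%, the chance of such a split verdict is 81.5% − 71.3% = 10.2% at 36 vs 36, and 6.3% averaged over simple randomization of 72.

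**Step 5: dependence on the primary contrast.** Section 2.0 states: "The primary end point will be the comparison of detection rates csPCa between arm A mpMRI+ and arm B". Section 9.0 states: "all procedures will be performed on an intention-to-treat basis for Aim 1 as our main analyses". These imply different comparisons. Section 9.0 gives the rates needed for both, "assuming about 25% of Arm A is MRI- and rate of csPCa was 4% in MRI- and 48% in MRI"-positive patients.

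- mpMRI-positive patients of arm A only: 0.75 × 36 = 27 vs 36, at 48.1% vs 18.1%. Two-sided Fisher power is 67.0%.
- Whole arm A: 0.75 × 48% + 0.25 × 4% = 37% vs 18.1%, at 36 vs 36. Two-sided Fisher power is 34.2%.

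**The case against.** The best counter-argument is that the two-sided sentence is general, the Aim 1 sentence is specific, and the hypothesis is directional. If the specific sentence governs, a one-sided Fisher test has 81.5% power at 36 vs 36 (80.7% averaged) and nothing is lost. That may be what was intended. However, the one-sided level appears only in the sizing sentence, and nothing carries it into the analysis.

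Four narrower points have some force.

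- The plan attaches 80% at 72 patients to Aim 2. For Aim 1 it claims a type II error of 0.20 at 62, so the like-for-like contrast is 63.5% at 31 per arm. The figure at 72 is the kinder one, because it credits Aim 1 with the patients added for Aim 2.
- An exact 36/36 split is a low point of a discrete test and occurs only 9.4% of the time. Nearby splits do better: 75.0% at 35/37, 76.7% at 37/35 and 77.2% at 34/38. About 74% is therefore the more representative figure, and 71% to 74% should be read as the balanced case and the average, not as a range of outcomes.
- At 80 evaluable, an individual split can reach 80% (41 vs 39 gives 80.9%). The shortfall holds for equal arms and on average, not for every possible allocation.
- The stricter test protects against false positives. That is true, and it limits the seriousness of the point.

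None of this removes the conflict between the sizing and analysis sentences.

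**Conclusion.** The concern holds. As written, the primary endpoint falls under a two-sided 5% Fisher exact test, while its sample size was justified for a one-sided 5% large-sample test. At 72 evaluable patients the power is 71.3% (36 vs 36) to 74.4% (averaged), about 6 to 9 points below 80%. If nobody is lost, the shortfall is about 1 to 4 points. At the 31 per arm quoted for Aim 1 it is 16.5 points.

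These figures take 48.1% vs 18.1% at face value, compare about 36 with 36, and use the usual Fisher two-sided p value, which sums all tables no more probable than the one observed. If the p value is instead defined by doubling the smaller tail, the average at 72 falls to 70.4%. Type I error is not inflated. The point should be fixed: it affects a headline design claim and leaves the decision rule for the primary endpoint ambiguous.

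**What to change.** In Section 9.0, name one test and one sidedness for the primary endpoint and use them for both sizing and analysis.

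- **Preferred:** keep the declared two-sided 5% Fisher test, delete the one-sided level from the Aim 1 sentence, and restate the power. For about 36 vs 36 at 48.1% vs 18.1%, that is about 71% to 74% at 72 evaluable (64% at 31 per arm).
- **Alternative:** if one-sided 5% is really meant for Aim 1, write that exception into the analysis sentence. Fisher then has about 81% at 72 evaluable, at the price of a weaker standard of evidence.

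Settle the primary contrast first and compute the power for that contrast, so that only one figure enters the protocol. On the plan's own rates it could be as low as 67% (mpMRI-positive patients only) or about 34% (whole arm A).

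The cost is one or two sentences and a restated power figure, with no extra patients and no change to procedures. Under the preferred route the sponsor has to report power below 80%. The choice should be recorded before any outcome data are examined.

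### Section 9.0 plans a two-sided Fisher p value for Aim 1 but no estimate or interval for the absolute gain in csPCa detection on which the trial is sized

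*Combined protocol and SAP*

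**What the plan says.** Section 9.0 (Statistical Considerations) of the combined protocol and SAP gives the analysis in two statements: "The associations between categorical variables and the arms will be analyzed with Fisher's exact test" and "p values will be obtained by the two-sided exact method at the conventional 5% significance level".

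The Aim 1 sample size rests on a quantity. The trial is "to detect a 30% absolute increase in the detection rate of csPCa", with "the rate of csPCa being 18.1% from standard biopsy", "with a one-sided 0.05 significant level, a type II error of 0.20"; on that basis "a sample size of 62 patients (31 per arm) will be required". The Aim 2 calculation asks for more men (72, or 36 per arm) and sets the total of 80 after 10% loss. Intention-to-treat is named as the main analysis for Aim 1.

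Section 2.0 words Aim 1 as a yes/no question: "Determine if UroNav increases the detection of csPCa between arm A mpMRI+ than arm B standard transrectal biopsy". Sections 2.0 and 5.0 describe the primary endpoint as a comparison of detection rates between arm A mpMRI+ and arm B. None of these sections names a risk difference, a ratio, an odds ratio or a confidence interval.

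**The concern.** The design asks how large the gain is, but the planned output says only whether a 5% threshold was crossed. In a trial this small the two come apart in both directions. A p value above 0.05 cannot show whether the planned 30-point gain has been excluded. A p value below 0.05 comes with an observed gain that had to be large to pass the test, and nothing planned shows how uncertain that gain is. The conclusion that readers carry into practice, in the first comparison of this device by this route, would lack a prespecified size and precision. The trial is also un-blinded, so leaving the effect measure open allows it to be chosen after the data are seen.

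**Working it through.** **Inputs.** From Section 9.0: arm B rate 18.1%; planned gain 30 points, so 48.1% in arm A; one-sided 0.05 and 80% power for the design; two-sided Fisher at 5% for the analysis; 36 evaluable per arm; 80 randomized, so 40 per arm; 25% of arm A MRI-negative at 4% and the rest at 48%. From Section 1.0: 43.9% vs 18.1% in the cited randomized trial, a gain of 25.8 points.

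**1. The plan's own figure.** Two-sample normal formula, pooled variance under the null, one-sided:

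n = [1.645 × √(2 × 0.331 × 0.669) + 0.842 × √(0.181 × 0.819 + 0.481 × 0.519)]² / 0.30² = (1.095 + 0.531)² / 0.09 ≈ 29.4, so 30 per arm.

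The plan's 31 per arm is reproduced to within one man per arm. Also 72 / 0.90 = 80, as stated.

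**2. Whole-arm gain implied by the Aim 2 inputs.** 0.25 × 4% + 0.75 × 48% = 37.0%, and 37.0 - 18.1 = 18.9 points.

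**3. Gain needed for significance.** All outcomes at 36 per arm were enumerated, with a two-sided Fisher p for each. For 5, 6, 7 or 8 arm B cases (13.9% to 22.2%), arm A needs at least 14, 15, 16 or 17 cases. Each is an excess of 9/36 = 25.0 points. At 40 per arm the threshold is 9/40 = 22.5 points for 5 to 7 arm B cases, and 25.0 for 8. At 31 per arm it is 25.8 to 29.0.

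**4. Power and mean observed gain among trials significant in favour of arm A** (36 per arm, 18.1% in arm B):

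| True arm A rate | True gain | Power | Mean significant gain | Ratio to truth |
|---|---|---|---|---|
| 48.1% | 30.0 | 71% | 35.0 | 1.17 |
| 43.9% | 25.8 | 58% | 32.8 | 1.27 |
| 37.0% | 18.9 | 34% | 29.9 | 1.58 |

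The 71% falls short of the planned 80% even with more than 31 men per arm, because the design used a one-sided test and the analysis is a two-sided Fisher test.

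**5. What an interval would add** (Newcombe 95% intervals, 36 per arm):

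- 13 vs 7 cases: difference 6/36 = 16.7 points, p = 0.19. The Wilson limits are 22.5% to 52.4% (arm A) and 9.8% to 35.0% (arm B). Lower limit: 0.167 - √[(0.361 - 0.225)² + (0.350 - 0.194)²] = -0.04. Upper limit: 0.167 + √[(0.524 - 0.361)² + (0.194 - 0.098)²] = +0.36. The planned 30 points lies inside.
- 16 vs 7 cases: 9/36 = 25.0 points, p = 0.042, interval +3.4 to +43.7.

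**6. How often a non-significant result leaves the target open.** At a true 30 points, 29% of trials are non-significant, and in 90% of those the upper limit still reaches 30. At 25.8 points the figures are 42% and 84%.

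**7. Agreement of p and interval.** For 14 vs 6 cases, Fisher's p is 0.064 while the Newcombe interval is +1.5 to +40.7. The two can disagree near 0.05, so one must be named as decisive.

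**The case against.** The strongest reply is that the overstatement is a matter of sample size and of conditioning on significance, not of a missing interval. That is right: with an interval added, the mean significant gain at a true 18.9 points is still 29.9. The interval shows the imprecision and no more.

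Four stronger readings are tempting, and the documents do not support them:

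- **That a significant result must overstate the gain.** It does so on average. At the planned 30 points, about 25% of significant trials understate it, and a significant 25-point result would itself be too low.
- **That 25 points is a fixed floor.** It belongs to 36 per arm with 5 to 8 arm B cases, which has a probability of about 61% at a rate of 18.1%. With 0 to 4 cases the floor is 16.7 to 22.2 points.
- **That the plan will declare no gain when p >= 0.05.** No such rule is written. This is a risk of interpretation, which the yes/no wording of Aim 1 makes easier.
- **That no magnitude will be visible.** A comparison of detection rates implies that both rates would be shown, so a reader could subtract them. The planned estimate and its precision are what is missing.

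It can also be said that the compared groups are unsettled. This stands. The calculations above use the whole of arm A; with about 27 mpMRI+ men (75% of 36) against 36, the floor runs from 23.1 to 29.6 points for 5 to 8 arm B cases. Finally, the interval can be computed from the same 2×2 table at reporting. That is true, but it would then be chosen after the data are known.

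**Conclusion.** The point holds in a limited form. The planned Fisher test is valid, but Section 9.0 provides no estimate or interval for the 30-point gain that justifies the trial's size. As a result, a non-significant trial could not be shown to have excluded its own target, and usually would not have. A significant trial would carry an interval about 40 points wide and an estimate that is modestly high on average if the true gain is 30 points, and markedly high if it is near 19.

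The figures assume 36 evaluable men per arm, 18.1% in arm B, and the whole of arm A compared with arm B. With 40 per arm the pattern remains but is weaker: if the true gain is 18.9 points, significant results average 28.5. This is a change that should be made; it does not invalidate the design.

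**What to change.** In Section 9.0:

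1. Name the risk difference in csPCa detection with a 95% CI as the primary estimate, and fix the interval method in advance.
2. State that it compares all of arm A with arm B by intention-to-treat, the analysis that Section 9.0 already calls the main one, and reconcile this with the mpMRI+ wording of the primary endpoint and Aim 1 in Sections 2.0 and 5.0.
3. State that Fisher's two-sided p decides whether an increase is claimed and that the CI describes its size. Alternatively, take the p value and the CI from the same exact method, so that they cannot disagree.
4. Read p >= 0.05 as inconclusive unless the upper limit is below 30 points. In that case the planned gain is excluded, which is not the same as showing no gain.
5. Give the same estimate and CI for overall PCa detection.

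The cost is a few sentences and an option in the SAS 9.4 software already planned, with no extra patients or data. The downside is that an interval of about ±20 points becomes visible and the claim is more modest. The change does not correct the upward bias of significant results, which comes from the trial's size.
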